Prior to the first ECT treatment all patients in both groups will be offered an MRI scan. The scanning at MUSC will be done on a research dedicated 3T Siemens scanner across the street from the Institute of Psychiatry. At GRU scanning will be done on a 3-T Philips Scanner. In addition to a high resolution structural scan (to be used for potential modelling of current flow), patients will also have an 8 minute resting BOLD scan for assessing functional connectivity. The entire non-contrast scan will take about 30 minutes. This will be repeated as well within 24-96 hours of the last ECT session of the course. MRI scanning details follow, although these may change over time as the technology advances without requiring an amended IDE as they pose no safety issue.

High-resolution structural images will be acquired using T1-weighted magnetization-prepared rapid-acquisition gradient echo (MPRAGE; FOV 256mm by 256 mm; voxel size: 1x1x2mm, with 0 mm gap; TR=7.5s, TE=3.7ms, flip angle=8°).

T2-weighted functional images will be acquired with a gradient-echo echo-planar imaging (EPI) sequence (TR=2 sec, TE=29 ms, flip angle=75, 64x64 acquisition matrix, 3.75 x 3.75 x 4.55 mm voxel size, FOV=240 mm, 3.5mm slice thickness, 1mm gap). Resting state scans will be acquired over a minimum of 5 min, 16 s in duration (158 volumes).

Subjects will be instructed to keep their eyes open during the scan and stare passively at a fixation cross. Their head will be restricted with foam cushions in order to minimize head motion.

fMRI Image processing and motion correction

Artifact Detection Tools (ART, http://www.nitrc.org/projects/artifact_detect) software will be used for automatic detection of the global mean and motion outliers in the functional data.

We will exclude from the analyses individual volumes from the time series if head displacement from the median head position was greater than 1.5 mm, or if head rotation from the median head position was greater than 0.5 degrees. The functional images will be pre-processed with SPM8 (<http://www.fil.ion.ucl.ac.uk/spm/>). Slice timing correction will be applied to the data to remove signal variation due to slice acquisition temporal onset differences. The first functional image volume of each participant will be used to determine parameters for spatial normalization into Montreal Neurological Institute (MNI) standardized space employed in SPM8 using non-linear transformation.

Functional Connectivity Analysis

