The four-lead EEG digitized at each treatment will be subjected to a FFT after artifacting, and power computed in 4 frequency bands, as well as total power across bands. The baseline, tonic, clonic and postictal epochs will be averaged separately. After testing for multivariate normality, MANCOVAs will be applied to the ictal and postictal power (\log_{10}) values, using Site and Treatment Group as between-subject factors, and age as a covariate. Hypotheses 2a and 2b call for opposite main effects in the ictal and postictal analyses. Hypotheses 2c and 2e predict an interaction between Treatment Group and the laterality repeated measures factor. Thus, an asymmetry index $[(r-l)/(r+l)]$ will be greater with FEAST than conventional stimulation. Similarly, Hypotheses 2d and 2e calls for an interaction between Treatment Group and frontal vs. temporal lead placement. Finally, Hypothesis 2f states that measures of ictal and postictal power have at most weak relations with efficacy. Percent change

in HRSD₂₄ scores will be added to the MANCOVAs as a covariate. Main effects of clinical improvement and first and second-order interactions will be modeled.

Hypothesis 3. In contrasting resting fMRI data, both FEAST and UB RUL ECT result in a reduction of (heightened) frontal connectivity, replicating previous findings (Abbott et al., 2013, Beall et al., 2012, Perrin et al., 2012). However, this effect is especially focal within the FEAST group, and more restricted to right frontal regions.

MANCOVAs will be conducted with Site and Treatment Group as between-subject factors, age as a covariate, and time (pre-post) and connectivity values in a priori brain regions as repeated measures factors.

Hypothesis 4. Efficacy as assessed immediately following the treatment course does not differ between the FEAST and UB RUL ECT groups.

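### Hypothesis 3 (resting fMRI) has no rule keeping a patient's two scans on one sequence and no model term for head motion below the exclusion limits

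*Combined protocol and SAP*

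**What the plan says.** **Acquisition.** Section IV.B.5a offers every patient in both groups a scan before the first treatment and another 24 to 96 hours after the last. MUSC uses a Siemens 3T scanner and GRU a Philips 3T. The scanning details are given with the proviso that "these may change over time as the technology advances without requiring an amended IDE as they pose no safety issue". No text says that a patient's two scans must share a sequence, and no record of sequence version is planned.

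**Run length.** The section plans that "patients will also have an 8 minute resting BOLD scan for assessing functional connectivity" and later sets a floor: "Resting state scans will be acquired over a minimum of 5 min, 16 s in duration (158 volumes". The functional sequence is given as "TR=2 sec, TE=29 ms, flip angle=75".

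**Motion.** At acquisition, "Their head will be restricted with foam cushions in order to minimize head motion". In processing, artifact-detection "software will be used for automatic detection of the global mean and motion outliers in the functional data". Individual volumes are then excluded "if head displacement from the median head position was greater than 1.5 mm", or if rotation from that position exceeds 0.5 degrees. The text names no realignment step, motion regressors or motion covariate.

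**Model.** Under Hypothesis 3 in Section IV.B.15, "MANCOVAs will be conducted with Site and Treatment Group as between-subject factors, age as a covariate, and time (pre-post) and connectivity values" in pre-chosen regions as repeated measures. The Statistical Analysis paragraph of IV.B.5a gives the same model. It adds a correlation of connectivity change with symptom change across all subjects, with no covariate named.

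**The concern.** Hypothesis 3 makes two claims. The first is a pre-post fall in frontal connectivity in both groups. No untreated group is scanned, so anything that shifts the second scan relative to the first is read as treatment. The second is that the fall is more focal with FEAST than with ultrabrief right unilateral ECT. Those groups are not randomized, so equal motion in the two cannot be presumed.

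Two scan-related routes are left open. If the sequence changes between one patient's two scans, that patient's change score contains the sequence effect as well as the treatment effect. If patients move systematically more or less after the course than before it, or if this change differs between the groups, motion that passes the exclusion limits enters the connectivity estimate and no model term can absorb it. The plan's own exclusion rule shows that its authors regard motion as able to distort these data.

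**Working it through.** **1. The plan's own figure.** Volumes = run time / TR. For the floor, (5 × 60 + 16) / 2 = 316 / 2 = 158, as stated. For the 8-minute target, 480 / 2 = 240. The 240 is derived; the protocol states no maximum.

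**2. What run length does.** The sampling SE of a Fisher-z correlation is 1/√(N − 3), treating volumes as independent.
- 158 volumes: 1/√155 = 0.080.
- 240 volumes: 1/√237 = 0.065.
- Variance ratio: 237/155 = 1.53.
- SE of a pre-post difference, √[1/(N₁ − 3) + 1/(N₂ − 3)]: 0.092 (240 and 240), 0.103 (158 and 240), 0.114 (158 and 158).

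A simulation at an assumed true correlation of 0.4 gave mean z of 0.425 at 158 volumes and 0.424 at 240. Run length changes the noise and leaves the mean where it was.

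**3. How many patients one sequence change could affect.** Inputs: three treatments a week (IV.B.6); a median of 10 sessions in the earlier FEAST series (III.D.6); second scan up to 96 hours after the last treatment; 3 years to completion (opening of Section IV); 40 completers per group (IV.B.1). Even accrual over 104 to 156 weeks is assumed.
- Interval between scans: 10/3 + 4/7 ≈ 3.9 weeks.
- Fraction affected: 3.9/156 = 2.5% to 3.9/104 = 3.8%.
- Of 80 patients: 2 to 3. For courses of 6 to 14 sessions the range is 1.3 to 4.0.

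**4. Effect on the test.** For a mean shift of δ SD of the change score, the two-sided false-positive rate is Φ(k − 1.96) + Φ(−k − 1.96). Here k = δ√80 for the time effect and k = δ/√(2/40) for a difference between groups of 40. The 5% level and all shifts are assumptions, since the protocol gives no alpha, SD or effect size for Hypothesis 3.

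*Sequence change.* With 2.5% of patients shifted by 1 SD, δ = 0.025 and k = 0.22, so the rate is 5.6%. It reaches 14.5% only if 10% of patients are affected.

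*Residual motion.*

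| δ (SD) | Time effect, n = 80 | Group contrast, 40 vs 40 |
|---|---|---|
| 0.1 | 14.5% | 7.3% |
| 0.2 | 43.2% | 14.5% |
| 0.3 | 76.5% | 26.9% |

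In the time column every patient's change is shifted by δ on average. In the group column the shift differs between groups by δ.

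**5. What the exclusion rule lets through.** The rule measures distance from the median head position. Two consecutive volumes on opposite sides of it can both be kept while lying almost 2 × 1.5 = 3 mm apart, against an in-plane voxel of 3.75 mm. Movement from one volume to the next is not limited directly.

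**The case against.** The other side has several good arguments, and most of them stand.

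- A reader might infer that the plan ignores head motion. It does not: cushions, outlier detection and volume exclusion are all specified. What is missing is an adjustment for the motion that remains.
- A reader might infer that runs of unequal length create a false change. They do not (step 2). A target and a floor are also compatible with each other.
- A reader might infer from the change clause that patients' paired scans will differ. The clause concerns IDE amendments and plans no such thing; it merely fails to prevent it. A single change would touch few patients. A stable sequence difference between early and late patients largely cancels in within-patient change, and a change that hits both groups equally does not bias the FEAST contrast. Site, and with it the scanner vendor, is already in the model.
- The motion shifts are assumed. Nothing in the documents gives their size or direction.
- Sections IV.B.5, IV.B.6 and IV.B.13 put the ictal EEG comparison first. MRI is offered and may be declined (IV.C.2), so fewer than 80 patients may be scanned.

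These points limit the concern without removing it. Resting fMRI is one of the two main methods for the focality objective in Section II, and Hypothesis 3 is among the hypotheses that IV.B.15 assigns to the primary analyses. Its time effect has no untreated comparison, and its group contrast has no randomization to balance motion.

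**Conclusion.** The point holds in limited form. Nothing keeps a patient's two scans on one sequence, and motion within the 1.5 mm and 0.5 degree limits has no term in the Hypothesis 3 model or in the connectivity-symptom correlation. A scan-related contribution to the pre-post change, or to the group difference, therefore cannot be separated from treatment.

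Of the two routes, the sequence change is minor: about 2 to 3 of 80 patients for one change under even accrual, and a false-positive rate of 5.6% against 5% if 2.5% of patients shift by 1 SD. Residual motion could matter more, but its size is unknown; the rates in step 4 show sensitivity and are not estimates. Run length affects precision only. The change is worth making because it is cheap and because mismatched scans cannot be fully repaired afterwards, but it does not touch the trial's primary aim.

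**What to change.** In IV.B.5a, require the same scanner, sequence and run length for both of a patient's scans. Allow a sequence change only between patients, log the sequence version for every scan, and include it as a factor in the Hypothesis 3 model.

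In IV.B.15, adjust Hypothesis 3 for residual head motion, using the per-volume displacement estimates that the exclusion rule already needs. Motion per scan varies over time, which the planned MANCOVA does not take directly. Two forms would work: analyse change scores with the pre-post change in mean volume-to-volume motion as a covariate, or fit a mixed model with mean motion as a time-varying covariate. Make the same adjustment in the connectivity-symptom correlation. Truncating all runs to a common length is not needed.

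The cost is protocol and analysis-plan wording, with no added burden on patients. A site could not switch sequence partway through a patient's course, and the model would lose one or two degrees of freedom.

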Two approaches can be used to perform functional network connectivity: a model-free method and a model-dependent method using seed-based correlational techniques. The first method enables the exploration of connectivity patterns without the need of defining an a priori seed region. In contrast to seed-based methods, model-free methods are designed to look for general patterns of (unique) connectivity across brain regions. We will first proceed with a model-free method (Independent Component Analysis (ICA)) and then guided by the results we will perform a seed-based method to confirm those results

Independent Component Analysis (ICA)

As a model-free method, we will use Group ICA (Calhoun et al., 2001). It will be performed using the Group ICA fMRI Toolbox (GIFT) to identify distinct brain regions with temporally coherent (functionally connected) hemodynamic signal change (Calhoun et al., 2008).

Time Series

As a seed-based method, using an in house program in Matlab or the resting state version of the Matlab-based cross-platform software CONN (<http://www.nitrc.org/projects/conn>), time series from the resting state scans will be extracted from specific ROIs based on the ICA analysis results by averaging the time series of all voxels in the ROIs. After scaling and filtering steps performed across all

brain voxels, the resulting times series will be correlated with the resting-state time-series of all other voxels, resulting in a functional connectivity map (fcMap).

Statistical Analysis

As correlation analysis, we will correlate the change in functional connectivity measures with the change in symptom measures for all subjects.

A two-factor MANCOVAs analysis will be conduct with Site and Treatment Group as between-subject factors, age as a covariate, and time (pre-post) and connectivity values in a priori brain regions as repeated measures factors.

Hypotheses

In contrasting resting fMRI data, we hypothesize that both connectivity methods will show that both FEAST and UB RUL ECT treatments significantly reduce connectivity between frontal cortex structures, replicating previous findings (Perrin et al., 2012, Abbott et al., 2013). However, we hypothesize that this effect is especially focal within the FEAST group (that is, FEAST patients will show a greater reduction in hyper-connectivity than will UB RUL, and these changes will be more restricted to right frontal regions.

B.6 FEAST Procedures

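### The seed-based fMRI analysis takes its seeds from an ICA of the same scans, so it cannot confirm the ICA, and neither the ROI selection rule nor the H3 regions are stated

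*Combined protocol and SAP*

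**What the plan says.** Section IV.B.5a (Functional Connectivity Analysis) sets an order. Group ICA comes first, used "to identify distinct brain regions with temporally coherent (functionally connected) hemodynamic signal change". The seed step follows: "guided by the results we will perform a seed-based method to confirm those results". Under Time Series, the seed signals "will be extracted from specific ROIs based on the ICA analysis results". Each seed is then correlated with every other voxel to give a connectivity map.

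The same section, and Hypothesis 3 in Section IV.B.15, then specify a MANCOVA with "time (pre-post) and connectivity values in a priori brain regions as repeated measures factors". No region, atlas or coordinate is listed. The only anatomical content is the wording of H3, that "this effect is especially focal within the FEAST group, and more restricted to right frontal regions". The Hypotheses paragraph of IV.B.5a expects both approaches to give the same answer: "we hypothesize that both connectivity methods will show that both FEAST and UB RUL ECT treatments significantly reduce connectivity".

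IV.B.5a describes one scan before the course and one after it, offered to all patients. It mentions no hold-out sample, cross-validation or external data set. The introduction to hypothesis testing in IV.B.15 counts H3 among the primary analyses. It says Type I error will be protected by keeping those analyses few and clearly specified.

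**The concern.** Two measures of the same network, taken from the same scans, share the same sampling error. If the ICA shows a group difference by chance, a seed placed in that network will tend to show it too. Calling this confirmation gives a second line of evidence that does not exist.

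Also, H3 cannot be checked against a prior commitment, because the plan says neither how ROIs are picked nor which regions enter the MANCOVA. That falls short of the safeguard in IV.B.15. At stake is the focality claim: objective 2a in Section II makes resting fMRI one of two main methods for showing that FEAST is more focal.

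**Working it through.** The documents give no alpha, power, effect size or component count for H3, so there is no figure to reproduce.

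**Inputs.** From the documents: 40 patients per group as the target (IV.B.1), and one pre and one post scan each. Assumed: all 40 per group are scanned; two-sided alpha is 0.05; there are K = 5, 10 or 20 candidate components; and the correlation r between the ICA and seed measures of the same network is 0.4 to 0.9. The test is a two-group comparison of pre-post change, a simplification of the planned MANCOVA. There is no true effect.

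**1. Does agreement confirm?** Take one network, with no selection. The chance that a false-positive ICA difference is repeated by the seed measure, significant and in the same direction, is P(Z1 > 1.96 and Z2 > 1.96) / 0.025, where Z1 and Z2 are standard normal with correlation r.

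| r | Chance of false confirmation |
|---|---|
| 0.4 | 13% |
| 0.5 | 18% |
| 0.8 | 44% |
| 0.9 | 59% |
| independent data | 2.5% |

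Simulation at 40 per group (4,000 runs per cell) gave 17-22% at r = 0.5, 41-45% at 0.8 and 55-61% at 0.9. This result needs no assumption about how ROIs are chosen.

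**2. Type I error of the seed test, ROIs chosen blind to the contrast.** Selection carries no information about the group difference, so the expected rate is 5%. Simulation gave 4.6-5.9%. Choosing seeds on the contrast in half the patients and testing them in the other half gave 4.4-5.8%.

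**3. Type I error, ROI taken from the component with the largest group difference.** Let M be the largest of K independent |Z| values, with density K[2Φ(m) − 1]^(K−1) · 2φ(m). Given M = m, the seed statistic is normal with mean rm and variance 1 − r², apart from sign. The error rate is P(|seed statistic| > 1.96) averaged over M. With K = 1 the formula returns 5.0%.

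| K | r = 0.4 | r = 0.5 | r = 0.8 | r = 0.9 |
|---|---|---|---|---|
| 5 | 8.2% | 10.0% | 17.2% | 20.0% |
| 10 | 10.1% | 13.0% | 26.1% | 32.5% |
| 20 | 12.3% | 16.5% | 36.9% | 48.0% |

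For r from 0.4 to 0.8 the range is about 8-37%. Simulation at 40 per group agrees at r = 0.5 and 0.8: 10.8% and 16.6% (K = 5), 13.0% and 25.3% (K = 10), 16.4% and 36.6% (K = 20). If the components are themselves correlated at 0.5, these fall to 9.2% and 13.4%, 11.3% and 21.2%, and 13.3% and 27.2%.

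Group size hardly matters. With 20 scanned per group the rates at r = 0.5 to 0.8 run from 9.8% to 36.4%, so low MRI uptake neither causes nor cures the problem.

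**4. Upper bound without an ROI-level correction.** If K independent ROIs are each tested at 0.05, the chance of at least one false positive is 1 − 0.95^K: 22.6% for K = 5, 40.1% for K = 10 and 64.2% for K = 20.

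**The case against.** The strongest reply is that nothing in the plan says ROIs are picked on the treatment contrast. The ICA's stated purpose is to find coherent networks, and no group or time comparison is mentioned at that step. Seeding from component maps found that way leaves the group test valid. This stands, and a reader who infers that the plan does inflate Type I error goes further than the documents. It is equally true that the plan does not exclude contrast-driven selection. The only results the section predicts are treatment effects, so seeds guided by the results can be read that way.

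A second reply is that seeds and readout regions need not be the same: ICA-derived seeds could produce a whole-brain map from which pre-chosen frontal targets are read. So it would be too strong to say that the seed step contradicts regions named in H3. H3 names none, and the text can be reconciled. But the plan does not describe that arrangement or list any targets.

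A third reply is that the study is preliminary and that its stated primary aim concerns ictal EEG. That limits the weight resting on H3. It does not remove H3 from the primary analyses in IV.B.15.

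None of these replies rescues the claim of confirmation, which fails under either reading because the same scans are used twice.

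**Conclusion.** The seed analysis cannot independently confirm the ICA. If the ICA difference is a chance finding, the seed analysis would repeat it about 13-59% of the time for r of 0.4 to 0.9, against 2.5% in new data. The ROI selection rule is missing, and the a priori regions of the H3 MANCOVA are unlisted and sit uneasily with ICA-derived ROIs.

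Type I error for FEAST versus UB RUL ECT is about 5% under blind selection and about 8-37% under the largest-difference rule. That range depends on the assumed rule, K, r, alpha and number scanned. A reader might take 8-37% as the false-positive rate of H3 itself, but the documents do not support that. H3 is directional and confined to frontal and right-frontal change, so a chance winner elsewhere or in the wrong direction would not count for it, and the planned test is a MANCOVA with site and age. The defect is a specification gap that leaves inflation possible, together with a claim of confirmation that the design cannot support.

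**What to change.** In IV.B.5a and under Hypothesis 3:

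- List the frontal and right-frontal regions for the H3 MANCOVA, by atlas label or coordinates, before any analysis. Alternatively, state that seeds are selected from a group ICA blind to treatment group, time and outcome, and give the rule.
- Say whether the MANCOVA regions are the seeds or separate readout targets.
- State the ROI-level multiplicity correction. Fixing several regions in advance does not remove the need for it.
- Describe the ICA-guided seed analysis as a second, correlated measure rather than confirmation.
- Label as exploratory any ROI chosen after the treatment contrast has been seen.

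The cost is text in the analysis plan, with no new data or scans. The downside is that effects outside the fixed regions can only be reported as exploratory. Whether the connectivity reports cited for H3 give usable regions cannot be judged from these documents, so the investigators would need to check that when making the list.

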We do not anticipate that this form of ECT (unidirectional, ultrabrief pulse with spatial targeting) will have an adverse impact on efficacy, although this is not certain. Potential lack of efficacy likely constitutes the most significant risk of FEAST. Precautions have been taken in this protocol to mitigate this risk. First, patients who do show sufficient benefit after 5 treatments may receive a dosage increment, increasing the stimulus dose from 6xST to 9xST. In the community, dosing of UB RUL ST is often 8xST or more (e.g., (Loo et al., 2012)). Second, any patient who completes the research phase as a nonremitter will be offered a course of traditional ECT (UB RUL ECT, high dose RUL or BL ECT). Our preliminary experience in 35 patients clearly indicates that FEAST has potent antidepressant properties. We cannot, however, say with assurance that these properties are equivalent to traditional forms of ECT, without explicit comparison. This study provides important data in this respect, involving the first cotemporaneous comparison of FEAST and UB RUL ECT, albeit in a non-randomized and non-masked fashion. It is anticipated that the findings obtained here will provide the foundation for a subsequent RCT.

The protocol involves monitoring of objective and subjective side effects and includes provision for alternative treatment for patients who do not respond clinically. Although a large number of procedures are conducted, other than ECT, they are all noninvasive. Patients who consent to the protocol have the option of declining participation in specific procedures (e.g., fMRI studies), but can retain participation in the remaining procedures.

Finally, FEAST might present with two theoretical risks: superficial skin burn and intracerebral damage to excessive current density). The use of an electrode with small surface area could increase the impedance in the circuit and result potentially in skin burn or prevent the passage of the stimulus. This theoretical risk is minimized by the fact that the ECT device voltage limits and immediately aborts stimulus delivery when excessive impedance is encountered. In this protocol, we are requesting that the voltage/impedance

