The major risks of the research are those associated with receipt of ECT. The experimental treatment condition used here, FEAST, should have reduced risk of cognitive impairment compared to traditional forms of ECT. The use of a 0.3 ms pulse width has been shown to markedly reduce the cognitive side effects of ECT, with little impact on efficacy ([name], 2004a, [name] et al., 2008, Loo et al., 2012). FEAST will be administered in such a way that cognitive side effects should be less intense and/or persistent than that which regularly occurs with older methods that do not take into account variation in seizure threshold (American Psychiatric Association, 2001). The use of a unidirectional current and focal stimulation should contribute to further reductions in cognitive side effects, although this is not certain.

We do not anticipate that this form of ECT (unidirectional, ultrabrief pulse with spatial targeting) will have an impact on efficacy. Were there an effect, it is anticipated that this form of treatment would confer lesser benefit. Given this possibility, provision has been made to identify early patients who do not benefit sufficiently from FEAST and offer them alternative treatment. That treatment will intensify in a stepwise manner the form of ECT administered. Specifically, as clinically indicated, patients who show insufficient benefit will have the dosage of

the unidirectional, ultrabrief pulse stimulus increased (from 6xST to 9xST), followed by a switch to high dosage RUL ECT with wide pulse width (1 ms), followed by use of traditional bilateral ECT. Thus, the protocol involves close monitoring of objective and subjective side effects and includes provision for alternative treatment for patients who do not respond clinically to initial treatment assignment. All of the assessment procedures are noninvasive, with several specifically geared to track the effects of treatment on cognition. Patients who consent to the protocol have the option of declining participation in specific procedures (e.g., fMRI), but can retain participation in the remaining procedures. Explicit provisions have been made to identify and manage complications.

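### The correlation of connectivity change with symptom change pools all patients without adjusting for treatment group, site or age; this modestly dilutes a true link, and can mask or create one if symptom change also differs by group or site.

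*Combined protocol and SAP*

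**What the plan says.** The Statistical Analysis paragraph of Section IV.B.5a (MRI scan) says "we will correlate the change in functional connectivity measures with the change in symptom measures for all subjects". It mentions no covariate, stratification or within-group version. Section B.15 does not return to this correlation, so nothing later supplies the missing terms. The baseline comparison of sites and groups under Data Screening in B.15 states no consequence for it.

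Two neighbouring analyses are adjusted. For the fMRI group comparison (B.15, Hypothesis 3), "MANCOVAs will be conducted with Site and Treatment Group as between-subject factors, age as a covariate". For the question whether ictal and postictal EEG power relates to efficacy (B.15, Hypothesis 2f), percent change in HRSD24 is added to MANCOVAs that already contain site, treatment group and age.

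On the expected differences:

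- **Connectivity.** B.5a predicts that "FEAST patients will show a greater reduction in hyper-connectivity than will UB RUL".
- **Symptoms.** Hypothesis 4 in B.15 states: "Efficacy as assessed immediately following the treatment course does not differ between the FEAST and UB RUL ECT groups". The risk sections are more guarded. C.2 says "Potential lack of efficacy likely constitutes the most significant risk of FEAST", and C.5 says "Were there an effect, it is anticipated that this form of treatment would confer lesser benefit".
- **Scanners.** "The scanning at MUSC will be done on a research dedicated 3T Siemens scanner", whereas "At GRU scanning will be done on a 3-T Philips Scanner".

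**The concern.** A correlation over two pooled groups combines two things: the patient-level relation within each group, and the relation between the group means. Only the first shows whether patients whose connectivity falls more also improve more. If group means differ on one variable only, the extra spread dilutes the within-group correlation. If they differ on both, the group means themselves contribute a correlation, which can offset a true link or imitate one. The same applies to site.

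The protocol predicts a group difference in connectivity change, so at least the first mechanism is to be expected. A difference in symptom change is not predicted but cannot be excluded. Allocation is non-randomised. The matching described in the study overview before Section IV.B covers gender, diagnosis, age and baseline mMMS, but not medication resistance. Section III.B.1 gives ECT response rates of 80–90% without adequate medication failure and 50–60% after it, and the Hypothesis 4 model adjusts for medication resistance.

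At stake is how readable the link between the proposed mechanism and clinical improvement will be.

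**Working it through.** The plan gives no target correlation, effect size, alpha or power for this analysis, so there is no figure to reproduce. The effect sizes below are assumptions, shown as ranges.

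**Inputs**

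- n = 80: 40 FEAST and 40 UB RUL ECT patients (study overview and B.1). MRI may be declined (C.2, C.5), so n = 60 and n = 40 are also shown.
- Equal group shares, p = 0.5.
- d_c: group difference in connectivity reduction (FEAST minus UB RUL), in within-group SDs. The direction comes from B.5a; the size, 0.5 to 1.0, is assumed.
- d_s: group difference in symptom improvement. It is 0 under Hypothesis 4, and −0.3 to −0.8 is assumed for the lesser-benefit contingency in C.5.
- True within-group correlation r_w: 0 or 0.30 (assumed). Two-sided alpha is 0.05 (assumed).

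**Formulas**

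r_pooled = [r_w + p(1−p)·d_c·d_s] / √{[1 + p(1−p)·d_c²]·[1 + p(1−p)·d_s²]}, with p(1−p) = 0.25.

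Rejection rate = Φ(−1.96 + m) + Φ(−1.96 − m), with m = atanh(r)·√(n−3).

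Unadjusted and undiluted, r = 0.30 and n = 80 give m = 0.3095 × 8.775 = 2.716, so power is 77.5%.

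**A. The protocol's own hypotheses (d_s = 0).** With r_w = 0 the numerator is 0, so there is no false link and rejection stays at 5%. With r_w = 0.30:

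| d_c | r_pooled | Power, n = 80 (undiluted 77.5%) | n = 60 (64.7%) | n = 40 (46.9%) |
|---|---|---|---|---|
| 0.5 | 0.30/√1.0625 = 0.291 | 74.9% | 61.9% | 44.6% |
| 0.8 | 0.30/√1.16 = 0.279 | 70.9% | 57.9% | 41.3% |
| 1.0 | 0.30/√1.25 = 0.268 | 67.5% | 54.6% | 38.7% |

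**B. FEAST also less effective (d_c = 0.8, n = 80).** For example, with d_s = −0.5 the between-group term is 0.25 × 0.8 × (−0.5) = −0.10 and the denominator is √(1.16 × 1.0625) = 1.110. This gives −0.10/1.110 = −0.090 when r_w = 0, and 0.20/1.110 = 0.180 when r_w = 0.30.

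| d_s | r_pooled if r_w = 0 | False-positive rate | r_pooled if r_w = 0.30 | Power |
|---|---|---|---|---|
| −0.3 | −0.055 | 7.7% | 0.220 | 50.2% |
| −0.5 | −0.090 | 12.4% | 0.180 | 35.9% |
| −0.8 | −0.138 | 23.0% | 0.121 | 18.6% |

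**C. Site (simulation, 20,000 runs, n = 80)**

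- A site shift of 0.8 SD in connectivity change only, with d_c = 0.8 and d_s = 0: no false link; 0.30 becomes 0.258 and power is 64.9%.
- Site shifts in both changes (0.8 and −0.5) on top of d_c = 0.8 and d_s = −0.5: the false-positive rate is 31.7% and power for 0.30 is 9.6%.
- A 1.5-fold difference in scanner gain alone: 0.30 becomes 0.294, with no false link.

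**D. After adjustment.** In the same simulations, a partial correlation given group and site keeps false positives at about 5%. In the scenarios with mean shifts and a true 0.30, the mean estimate stays at about 0.30 and power at about 77%. Age was not simulated.

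**The case against.** The strongest reply is that this is one sentence about an exploratory analysis. B.15 confines the primary analyses to its listed hypotheses. Hypothesis 3 is tested by the adjusted MANCOVA, the main aim is ictal EEG, and no threshold or decision attaches to the correlation. That stands, and it limits the point to a low-priority improvement.

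The reply also corrects several stronger readings that a reader might infer:

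- **That the differences the protocol anticipates would create a false link.** A false link needs a group or site difference in both variables. The protocol predicts only the connectivity difference and hypothesises equal efficacy. Naming lack of efficacy as the main risk, as C.2 does, is not predicting it; that section also says no adverse impact on efficacy is anticipated, while conceding uncertainty.
- **That the artefact would falsely support the mechanism.** In the only contingency the documents name, FEAST confers less benefit, so the spurious correlation is negative. A spurious positive one would need FEAST to be the more effective treatment, which is nowhere predicted.
- **That two scanner makes bias the correlation in themselves.** The variable is change within a patient. If both of a patient's scans come from the same site's scanner, as B.5a implies, a fixed offset cancels, and a gain difference has little effect. Site matters mainly when mean connectivity change and mean symptom change both differ by site.

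The reply does not justify the omission. No reason is given for dropping terms that the two comparable analyses keep. Section III.D.2 also acknowledges that equal efficacy has not been established without a masked, randomised comparison.

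**Conclusion.** The point holds as a modest analysis weakness. The pooled correlation is unadjusted where its neighbours are adjusted. Under the protocol's own hypotheses it loses about 3–11% of a true correlation of 0.30 (1 − 0.291/0.30 = 3%; 1 − 0.268/0.30 = 11%) and between about 3 and 10 percentage points of power at n = 80 (77.5 − 74.9 = 2.6; 77.5 − 67.5 = 10.0). It produces no false link.

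The larger errors in part B of the working arise only if symptom change also differs by group, or if both changes differ by site. The non-randomised design makes that plausible, but the protocol does not predict it. These sizes rest on assumed differences in SD units, equal group sizes, a true correlation of 0.30 and full MRI uptake; the documents give no values for the effect sizes or the uptake. No primary conclusion is affected.

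**What to change.** In Section IV.B.5a, replace the pooled correlation with a partial correlation, or a regression of symptom change on connectivity change, adjusted for treatment group, site and age. Report the group-by-connectivity interaction and the estimate within each treatment group, so that a reader can see whether the relation is shared. Repeat the sentence in B.15 so that the analysis appears in the statistical plan.

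The cost is a short addition to the text and about three degrees of freedom, with no new data. When there are no group or site differences, adjusting for group and site lowered simulated power for a true 0.30 only from 77.9% to 76.7%.
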